7.2 Data and Statistical Analysis

Patient cohort 1:

For the primary outcome, SSI is the dependent variable and bone and tissue perfusion, as measured by ICG fluorescence, is the independent variable. Unplanned fracture-related reoperation is the secondary dependent variable and bone and tissue perfusion as measured by ICG fluorescence, is the independent variable. Descriptive statistics, including means and standard deviations, will be presented with 95% confidence intervals. To select the most important ICG fluorescence kinetic curve-related variables, we will perform a bivariate analysis evaluating whether each variable predicts infection and we will select the variable with the highest individual area under the receiver operating curve (AUC ROC).

Our primary null hypothesis is that the post-debridement maximum ICG intensity ($I_{max-post}$) among patients with SSI is equal to or greater than that in the non-SSI patient group. The primary alternative hypothesis is that $I_{max-post}$ in the SSI group is smaller than that in the non-SSI group. We will then perform Students t-tests and chi-square analyses (depending on continuous or categorical variable status) to determine unadjusted associations between the most important ICG fluorescence variable and SSI. A p-value of 0.05 or less will be considered significant for differences between SSI and non-SSI groups. We will then apply multiple logistic model including ICG fluorescence and previously identified predictors for SSI³⁷⁻³⁹. Wald test will be used to determine if ICG fluorescence or any other predictors are significant in the model. We set the type I error at 5%. Table 7.1 shows a summary of the study outcomes, corresponding

hypotheses, and method of analysis to be performed. We anticipate that we will demonstrate a statistically significant difference between the maximum post-debridement ICG fluorescence in patients with and without SSI

Table 7.1 Summary of Outcome Analysis Plan for patient cohort 1

Objective	Outcome		Hypothesis	Method of analysis
	Name	Type		
Determine the association between post-debridement bone perfusion as measured by quantitative ICG fluorescence and surgical site infection (SSI) in patients with open fracture	SSI	Binary	Mean perfusion will be lower among patients who develop SSI	Students t-test Multivariable logistic regression
	Unplanned fracture-related reoperation	Binary	Mean perfusion will be lower among patients who require unplanned fracture-related reoperation	Students t-test Multivariable logistic regression

Patient cohort 2:

For the primary outcome, treatment failure will be the dependent variable and bone and tissue perfusion, as measured by ICG fluorescence will be the independent variable. Descriptive statistics, including means and standard deviations, will be presented with 95% confidence intervals. To select the most important ICG fluorescence kinetic curve-related variables, we will perform a bivariate analysis evaluating whether each variable predicts infection and we will select the variable with the highest area under the curve (AUC).

Our primary null hypothesis is that the post-debridement maximum ICG intensity ($I_{max-post}$) among patients with persistent SSI/treatment failure is equal to or greater than that in the non-persistent SSI/non-treatment failure patient group. The primary alternative hypothesis is that $I_{max-post}$ in the persistent SSI/treatment failure

group is smaller than that in the non-persistent SSI/non-treatment failure group. We will then perform a Students t-test to determine the association between the most important ICG fluorescence variable and persistent SSI/treatment failure. A p-value of 0.05 or less will be considered significant for differences between persistent SSI/treatment failure and non-persistent SSI/non-treatment failure groups.

We will then apply multiple logistic model including ICG fluorescence and previously identified predictors for persistent SSI/treatment failure³⁷⁻³⁹. Wald test will be used to determine if ICG fluorescence or any other predictors are significant in the model. We set the type I error at 5%. Table 7.2 shows a summary of the study outcome, corresponding hypotheses and method of analysis to be performed. We anticipate that we will demonstrate a statistically significant difference between the maximum post-debridement ICG fluorescence in patients who fail treatment for their SSI resulting in persistent SSI/treatment failure and those who do not.

For subset cohort 2-1, for each DCE-MR and DCE-FI parameter, statistics of median and percentiles will be calculated for each of ROIs. Due to the small cohort size, the correlations between DCE-MRI and DCE-FI will be utilized to analyze the data of each corresponding ROI, assuming that all ROIs in each subject were independent⁴⁰.

Table 7.2: Summary of Outcome Analysis Plan of patient cohort 2.

Objective	Outcome		Hypothesis	Method of analysis
	Name	Type		
Determine the association between post-debridement bone perfusion as measured by quantitative ICG fluorescence and persistent SSI/treatment failure in patients with SSI	Persistent SSI/Treatment failure	Binary	Mean perfusion will be lower among fracture patients with persistent SSI/treatment failure	Students t-test Logistic regression

Patient cohort 3: Classification into cohort categories (closed fracture, open fracture, complication) is the independent variable and ICG fluorescence magnitude is the dependent variable. Descriptive statistics, including means and standard deviations, will be presented with 95% confidence intervals.

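### Section 7.2 does not say whether the primary t-test in cohorts 1 and 2 is on I_max-post or on the variable with the best AUC in the same patients; only the first keeps 5%, and Student's test does not suit the planning SDs.

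*Combined protocol and SAP*

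**What the plan says.** The cohort 1 text in section 7.2 runs in this order.

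1. Each ICG kinetic-curve variable is assessed as a predictor of infection: "we will select the variable with the highest individual area under the receiver operating curve (AUC ROC").
2. The hypotheses follow: "Our primary null hypothesis is that the post-debridement maximum ICG intensity" is equal or greater in the SSI group, against the alternative that it is smaller.
3. Then comes the test: "We will then perform Students t-tests and chi-square analyses (depending on continuous or categorical variable status"), used "to determine unadjusted associations between the most important ICG fluorescence variable and SSI". A p-value of 0.05 or less is significant, and type I error is set at 5%.

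Cohort 2 repeats the sequence: "we will select the variable with the highest area under the curve (AUC"), hypotheses on I_max-post, then a Student's t-test "to determine the association between the most important ICG fluorescence variable and persistent SSI/treatment failure".

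Other text points to a fixed variable. The Table 7.1 objective is "Determine the association between post-debridement bone perfusion as measured by quantitative ICG fluorescence and surgical site infection (SSI"), and Table 7.2 has the matching objective for cohort 2. In both cohorts the anticipated result concerns maximum post-debridement fluorescence. The power statement in section 7.1 concerns I_max, without saying pre- or post-debridement.

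The plan gives no candidate list, hold-out sample or adjustment for selection, and section 7.3 analyses all patients. Section 7.2 does not state the sidedness of its t-test. The Study Summary (Statistical Considerations) adds unadjusted Pearson tests of pre-debridement, post-debridement and change values, a ROC threshold, and a search by AUC for the best property. It does not say whether these are exploratory.

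**The concern.** The test sentence takes up the label that the ranking step attaches to the winning variable, so a literal analyst would test the AUC winner. Choosing a variable because it separates the outcome groups, and then testing that separation in the same patients, generally makes the p-value too small and the AUC optimistic. The hypothesis sentence instead points to one fixed variable. A reader cannot tell which test carries the primary hypothesis, or whether the stated 5% and power apply to it.

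A second matter arises under either reading. Section 7.1 plans for the larger SD in the smaller group. Student's pooled-variance test understates the standard error in that setting.

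**Working it through.** **Inputs (section 7.1).** Cohort 1: 16 with SSI and 144 without. Cohort 2: 22 treatment failures and 52 non-failures. Difference 24 a.u.; SDs 30 (event group) and 15; type I error 5%. The SDs are taken as already including the 50% increase: raising them again to 45 and 22.5 gives two-sided Welch power of only 51% and 63%.

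**Step 1: the stated power.** Welch: SE = √(30²/n₁ + 15²/n₂), with Satterthwaite df and the noncentral t.
- Cohort 1: SE = √(56.25 + 1.5625) = 7.60; 24/7.60 = 3.16; df = 15.8; two-sided power 84% (stated 86%).
- Cohort 2: SE = √(40.91 + 4.33) = 6.73; 24/6.73 = 3.57; df = 25.6; two-sided power 93% (stated 93%).

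One-sided Welch gives 92% and 97%. Student's test would show about 98% in both cohorts by simulation. The stated figures therefore roughly fit a two-sided Welch test of one variable. A pooled test with the SDs reversed (15 in the event group) gives 88% and 94%, also close, but the cohort 1 text assigns 30 to the SSI group. For cohort 2 the assignment follows the order of the text.

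**Step 2: the AUC winner is tested.** Null simulation with equal SDs, the same outcome for ranking and test, and Welch at 0.05. The number of candidates and their correlation are assumptions. Ranges cover both cohorts; correlation is 0.5 to 0.9 for the 3- and 6-variable sets and 0 to 0.9 between the pre and post values.

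| Candidates (assumed) | Directional AUC, two-sided test | Directional AUC, one-sided test | Either-direction AUC, two-sided test |
|---|---|---|---|
| 3 variables | 5-7% | 8-12% | 8-13% |
| Pre, post and change of one parameter | 6-7% | 11-13% | 11-13% |
| 6 variables | 6-10% | 9-18% | 10-20% |

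Directional means ranked for lower values in the event group. With only two candidates, directional ranking and a two-sided test, the error stays near 5%; hence *generally*. With one variable fixed in advance and equal SDs, the simulated error is about 5%.

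**Step 3: outcome used for ranking in cohort 2.** Section 7.2 ranks by prediction of infection but tests persistent SSI/treatment failure, which section 3.2 allows to include persistent nonunion. Step 2 assumes one outcome, so inflation in cohort 2 may be smaller than shown.

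**Step 4: Student's test on one fixed variable, SDs 30 and 15, no true difference.** Student's SE is about √[s_p²(1/n₁ + 1/n₂)].
- Cohort 1: s_p² = (15×900 + 143×225)/158 = 289.1; SE ≈ 4.48 against a true 7.60, ratio 0.589. The critical value 1.975 acts as 1.975 × 0.589 = 1.16, a two-sided error of about 24%. Simulation: 24.8%.
- Cohort 2: s_p² = (21×900 + 51×225)/72 = 421.9; SE ≈ 5.22 against 6.73, ratio 0.777. The critical value 1.993 acts as 1.55, an error of about 12%. Simulation: 12.8%.
- Welch, simulated: 5.0% in both cohorts. These errors depend only on the 2:1 ratio.

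**The case against.** The strongest reply is that I_max-post is the better-supported reading. The hypotheses name it, the anticipated results concern maximum post-debridement fluorescence, the table objectives are limited to post-debridement perfusion, and the power statement covers I_max. Only the phrase defining the test points elsewhere. If I_max-post is tested regardless, the selection issue is unclear wording that one sentence would close. That stands, and it is why the selection point is conditional. It does not remove the point, because no passage says the ranking leaves the test variable unchanged.

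The size is also open to challenge. The only set the plan enumerates is pre, post and change, and it is listed for the Pearson analysis, not for the ranking. With that set, directional ranking and a two-sided test, the error is 6-7%. A reader might infer that the primary analysis is certainly data-selected and its error several times nominal. The documents do not support this: larger figures need candidate counts that the plan does not give, and the reading behind them is the less supported one.

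The Student's test figures rest on SDs derived from a porcine study, and on the 2:1 ratio holding in patients when there is no mean difference. They are independent of the selection question and should not be used to enlarge it. Finally, section 7.1 calls the work a pilot, and section 1.5.2 says no diagnostic or therapeutic decision rests on it. That limits the harm, but the plan still states a primary hypothesis, a 5% error rate and power.

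**Conclusion.** The concern holds in conditional form. Section 7.2 leaves two readings of the primary test in cohorts 1 and 2. Testing I_max-post regardless means the AUC ranking costs nothing in error rate. Testing the winner generally does not keep 5%: about 5-7% or 8-13%, depending on sidedness and ranking direction, for the three-candidate sets assumed above, and more with more candidates. The 86% and 93% power figures would then not describe the test. Cohort 2 inflation may be smaller because the ranking and testing outcomes differ as written.

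Under either reading, Student's test does not fit the plan's own SDs. If the 2:1 ratio holds, with the larger SD in the smaller group, its two-sided error on a single fixed variable is about 25% in cohort 1 and 13% in cohort 2, against 5% for Welch. This should be fixed, mainly by clarifying the wording; it does not show that the study's primary analysis is invalid.

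**What to change.** - State that I_max-post at the index study surgery is the single confirmatory variable in each cohort, tested once at 5% whatever the AUC ranking shows. The procedure must be named because section 6 images every repeat debridement.
- State the sidedness. Two-sided roughly fits the stated power.
- Replace Student's t-test with Welch's. The planned sample size need not change.
- Use I_max-post as the ICG term in the primary logistic model.
- Label the AUC ranking, the ROC threshold and the Study Summary's Pearson tests exploratory. Report the selected variable's AUC with a bootstrap optimism correction that repeats the selection in every resample.
- In cohort 2, align the ranking outcome with the tested outcome.
- Reconcile section 5.2, which allows a single imaging series, with section 4.5.1, which removes participants whose imaging is not completed. This decides who has I_max-post. Report the number without it by outcome group.

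The cost is SAP wording and a bootstrap routine. The downside is that a better-performing kinetic variable can be reported only as exploratory.

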Duration of administration	Patients are enrolled in the study from time of consent prior to surgery to the end of six months of the follow up period.
Reference methods	N/A
Statistical Considerations	Descriptive statistics will be present (mean and standard deviation) with 95% confidence intervals. We are planning to collect ICG data before and after the debridement. Pearson correlation between ICG parameters (pre-debridement, or/and post-debridement, or/and changes between pre- and post-debridement) and index infection/recurrent will be calculated for each of three patient cohorts. We will also include the corresponding coefficient of determination indicating how much variation in index infection/recurrent can be explained in ICG parameters. Finally, we will evaluate the significance of the correlation coefficient using two sided t-test. P-value less than 0.05 will indicate that the correlation is significant. Then, we will form receiver operating characteristic (ROC) curves to illustrate graphically the performance and to obtain the threshold for differentiating the recurrent infection from non-infection group, of each chosen model. Area under the ROC curve will be used to determine the optimal property for differentiating the recurrent infection patients from the non-infection patients.

1 Introduction

This document is a clinical research protocol and describes a human research study. This study will be conducted according to US and international standards of Good Clinical Practice (FDA Title 21 part 312 and International Conference on Harmonization guidelines), applicable government regulations and Institutional research policies and procedures. All personnel involved in the conduct of this study have completed human subject protection training and primary oncologic surgeons performing study procedures will be trained on this protocol

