7.1 Sample Size Determination

The participating Statisticians on the study are members of the Norris Cotton Cancer Center and/or Department of Orthopaedics at Dartmouth-Hitchcock Medical Center. Sample size determination is based on the primary objective of the study as a pilot assessment of ICG fluorescence intensity of bone perfusion.

For patient cohort 1, we anticipate that approximately 10% of patients with open fracture will have an SSI within 12 months of their fracture^{1, 2, 32}. A total sample size of 160 patients will result in an estimated 16 patients with an SSI and 144 patients without an SSI. We will have 86% statistical power to detect a mean maximum fluorescence intensity (I_{max}) difference of 24 (a.u.) between the SSI group and the non-SSI group with an estimated standard deviation of 30 (a.u.) and 15 (a.u.), respectively. All parameters were obtained from our previous porcine study. To be conservative, we increased the standard deviation by 50% for this power calculation. The type I error is set to be 5%. If we assume a drop-out rate of 10%, then a total of 176 patients will be enrolled.

For patient cohort 2, we anticipate approximately 30% of patients with an SSI will go on to develop a persistent SSI/treatment failure within 12 months of diagnosis of their SSI¹². Based on this estimate, a sample size of 22 patients with SSIs and 52 patients without, will have 93% statistical power to detect a mean I_{max} difference of 24 (a. u.) between the persistent SSI/treatment failure group and the non-persistent SSI/non-treatment failure group with I_{max} estimated standard deviation of 30 (a. u.) and 15(a. u.). All parameters are obtained from our previous porcine study, which are consistent with a pilot study conducted at STC in human participants using ICG fluorescence for a different indication. To be conservative, we increased the standard deviation by 50% for this study. The type I error is set to be 5%. If we assume the dropout rate is 10%, then a total of 82 patients will be recruited.

For patient cohort 2-1, the strength of the relationship between DCE-MR and DCE-FI measurements will

be assessed by determining the zero-order correlation and resulting R2 metric. A sample of 21 was estimated utilizing formula presented by Bonett & Wright ³⁶ with a Type I error rate of 0.05 and Type II error

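### Section 7.2 sets directional primary hypotheses at p of 0.05 or less without stating sidedness, while the power in 7.1 fits a two-sided 5% test and not a one-sided 5% test

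*Combined protocol and SAP*

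**What the plan says.** Section 7.2, cohort 1: the primary null is that Imax-post among patients with SSI "is equal to or greater than that in the non-SSI patient group". The alternative is that Imax-post "in the SSI group is smaller than that in the non-SSI group". The decision rule reads: "A p-value of 0.05 or less will be considered significant for differences between SSI and non-SSI groups". The test named is Student's t, with type I error 5%.

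Section 7.2, cohort 2: the null has the same form. Imax-post with persistent SSI or treatment failure "is equal to or greater than that in the non-persistent SSI/non-treatment failure patient group". The test and threshold are the same. Tables 7.1 and 7.2 also predict lower mean perfusion in the patients who do badly.

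Section 7.1 gives a 5% type I error for both cohorts, again without sidedness. For cohort 1 it says "We will have 86% statistical power" for a difference of 24 a.u.; for cohort 2 it gives 93% for the same difference.

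The only mention of sidedness is in the Study Summary, Statistical Considerations: "we will evaluate the significance of the correlation coefficient using two sided t-test". The coefficient is the Pearson correlation between ICG parameters and index or recurrent infection.

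**The concern.** Read literally, a null of equal or greater with an alternative of smaller, rejected at p of 0.05 or less, is a one-sided 5% test. Read by its reference to differences, the same rule is two-sided. The plan does not choose, and this is the primary decision rule in both powered cohorts.

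The choice can change the conclusion. If the observed difference is in the predicted direction, the one-sided p is half the two-sided p. A two-sided p of 0.08 is then significant under one reading and not under the other, and an analyst could defend either from the text. If the sample size was built on one cut-off and the hypotheses imply another, the stated power does not describe the test as written.

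**Working it through.** **Inputs (section 7.1).** Difference 24 a.u.; SDs 30 (event group) and 15 (non-event group); type I error 5%. Cohort 1: 16 with SSI, 144 without. Cohort 2: 22 and 52, taken as failures and non-failures. I take 30 and 15 as already including the 50% increase that 7.1 describes; the last step tests this.

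**Formulas.** SE = √(s₁²/n₁ + s₂²/n₂). Noncentrality δ = 24/SE. Welch–Satterthwaite df = SE⁴ / [(s₁²/n₁)²/(n₁−1) + (s₂²/n₂)²/(n₂−1)]. Power is the noncentral-t probability beyond the critical value.

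**Cohort 1.** SE = √(900/16 + 225/144) = √(56.25 + 1.5625) = 7.603. δ = 24/7.603 = 3.156. df = 15.8.

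**Cohort 2.** SE = √(900/22 + 225/52) = √(40.909 + 4.327) = 6.726. δ = 24/6.726 = 3.568. df = 25.6.

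| | Stated | Two-sided 5%, Welch | Two-sided 5%, normal | One-sided 5%, Welch | One-sided 5%, normal |
|---|---|---|---|---|---|
| Cohort 1 | 86% | 84.1% | 88.4% | 91.5% | 93.5% |
| Cohort 2 | 93% | 92.9% | 94.6% | 96.6% | 97.3% |

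Cohort 2 is reproduced by two-sided Welch. In cohort 1 the stated figure lies between the two-sided Welch and normal values, 1.9 points above the former. Both stated figures are below every one-sided 5% value. A one-sided 2.5% test gives the same power as two-sided 5%, so the calculation cannot separate those two.

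**What the cut-off means in a.u.** At these SEs, the observed difference needed for significance is:
- Cohort 1: 2.122 × 7.603 = 16.1 two-sided, against 1.747 × 7.603 = 13.3 one-sided.
- Cohort 2: 2.057 × 6.726 = 13.8 two-sided, against 1.707 × 6.726 = 11.5 one-sided.

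**Could another one-sided calculation give the stated figures?** With SDs 30 and 15, pooled variance gives 99.99% and 99.8% one-sided, and average variance gives 98.5% and 98.9%. A one-sided match appears only in cohort 2, and only after changing the SDs:
- Common SD of 30: 92.6% to 93.3% in cohort 2, but 89.9% to 91.8% in cohort 1.
- SDs 45 and 22.5, pooled: 91.8% in cohort 2, but 97.2% in cohort 1.

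No one-sided 5% setting tried fits both cohorts. If 30 and 15 are raised by a further 50%, Welch power is 50.7% two-sided and 64.4% one-sided in cohort 1, and 62.9% and 74.9% in cohort 2. Neither matches, so 30 and 15 are most likely the inflated values.

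**The named test.** Pooled Student's t assumes equal variances, but here the smaller group has the larger SD. In cohort 1 the pooled variance is (15 × 900 + 143 × 225)/158 = 289.1, so the pooled SE is √[289.1 × (1/16 + 1/144)] = 4.48, against a true SE of 7.60. Simulation with no true difference gives these rejection rates at nominal 5%:

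| | Two-sided, both directions | Two-sided, claimed direction only | One-sided |
|---|---|---|---|
| Cohort 1 | about 25% | about 12% | about 17% |
| Cohort 2 | about 13% | about 6% | about 10% |

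Welch under the same conditions gives about 5% two-sided, 2.5% in the claimed direction, and 5% one-sided.

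**The case against.** The strongest reply is that the plan nowhere says one-sided. It speaks of differences, it anticipates a statistically significant difference, and its one sidedness statement is two-sided. The power points the same way. On that view two-sided 5% was intended, the directional hypothesis is loose wording, and testing it two-sided is conservative. This is probably what was meant. But the reader has to infer it from the power calculation against the literal form of the null, and a primary decision rule should not rest on inference.

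Four further points limit the concern, and all stand:

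- The synopsis does not directly contradict 7.2. Its two-sided test is attached to a correlation coefficient, not to the comparison of mean Imax-post. The link is that the t-test of a Pearson correlation with a binary outcome is algebraically the pooled Student's t-test, so the same association could carry two p-values.
- A reader might infer that the primary error rate is wholly undetermined, or that it is simply 5% where it should be 2.5%. The nominal level is set at 5%, and only its sidedness is open. The 2.5% against 5% contrast holds for Welch and not for the Student's t-test that 7.2 names.
- A reader might infer that the trial could not report higher perfusion in infected tissue. The planned means, SDs and 95% confidence intervals would show it. A one-sided test only could not declare it significant.
- A directional hypothesis is legitimate here. Section 1.1 gives a rationale, and 7.1 describes a pilot assessment. The point is not that the direction should be dropped.

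**Conclusion.** The concern holds in a limited form. The directional hypotheses in 7.2, with p of 0.05 or less and no sidedness, are not aligned with the basis of the power in 7.1. That power is consistent with two-sided 5%, or equivalently one-sided 2.5%, using unequal variances. It is 5.5 points (91.5 − 86) and 3.6 points (96.6 − 93) below what one-sided 5% Welch would give. The practical consequence is confined to two-sided p-values between 0.05 and 0.10 in the predicted direction.

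This rests on SDs of 30 and 15 being the values used, on group sizes as planned, and on approximately normal intensities. The match in cohort 1 is close but not exact. The documents do not show that a one-sided test was intended.

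The choice between Student and Welch matters more for the actual error rate than the sidedness does: if the SDs are as assumed, settling sidedness alone would leave a pooled test at about 25% and 13%. Both should be corrected together, before outcome data are analysed.

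**What to change.** 1. In 7.2, state for cohorts 1 and 2 that the primary comparison is of mean Imax-post, tested two-sided at 5%. Keep lower perfusion as the expected direction and the scientific hypothesis.
2. In 7.2 and Tables 7.1 and 7.2, name the unequual-variance (Welch) t-test in place of Student's t.
3. In 7.1, state that the power figures assume a two-sided 5% unequal-variance test, and that 30 and 15 are the SDs after the 50% increase, if that is so.
4. State that 7.2 governs the primary inference and that the synopsis correlation is descriptive.

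The cost is wording in three places. Enrolment targets do not change, and the stated powers can stay or be refreshed to the Welch values of 84.1% and 92.9%.

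### Under section 7.1's own SDs, the named Student's t-test would reject equal means about 25% (cohort 1) and 13% (cohort 2) of the time two-sided, not 5%

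*Combined protocol and SAP*

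**What the plan says.** Section 7.1 sizes cohort 1 on "an estimated 16 patients with an SSI and 144 patients without an SSI", to detect a mean I_max difference of 24 a.u. "with an estimated standard deviation of 30 (a.u.) and 15 (a.u.), respectively". The order puts the SD of 30 in the SSI group. The stated power is 86% at a type I error of 5%. Cohort 2 is sized on "a sample size of 22 patients with SSIs and 52 patients without" (in context, with and without persistent SSI or treatment failure), with the same difference and SDs and a stated power of 93%. The SDs come from a porcine study, and section 7.1 adds: "To be conservative, we increased the standard deviation by 50% for this power calculation".

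For the analysis of cohort 1, section 7.2 says "We will then perform Students t-tests and chi-square analyses (depending on continuous or categorical variable status"), followed by "A p-value of 0.05 or less will be considered significant for differences between SSI and non-SSI groups". For cohort 2 it says "We will then perform a Students t-test to determine the association", and the method column of Table 7.2 reads "Students t-test Logistic regression". Table 7.1 names Student's test for both SSI and unplanned reoperation.

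For this comparison the document mentions no unequal-variance test, variance check, transformation or rank-based alternative. The hypotheses in section 7.2 are directional, but the sidedness of the t-test is not given there. Only the Study Summary (Statistical Considerations) mentions a two-sided t-test, and that is for a Pearson correlation between ICG parameters and infection.

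**The concern.** Student's t-test estimates one common variance. When the smaller group has the larger SD, the large low-variance group dominates that estimate, so the standard error of the mean difference is too small and the test rejects too often. Section 7.1 plans for exactly this arrangement in both cohorts.

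The t-test is a listed method for every outcome in Tables 7.1 and 7.2, and it tests the stated primary hypotheses at 5%. If it over-rejects, the study could report that perfusion differs between patients with and without SSI when mean intensity does not differ. Its confidence intervals would also be too narrow. That association is meant to support the secondary objective of building tools to guide debridement.

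**Working it through.** **Inputs (section 7.1).** Cohort 1: n₁ = 16 with SD 30, n₂ = 144 with SD 15. Cohort 2: n₁ = 22, n₂ = 52, same SDs. Difference 24, α = 0.05. The cohort 2 sentence does not say which group has which SD. The reverse order gives SE = √(225/22 + 900/52) = 5.25 and two-sided Welch power of 99.5%, so only SD 30 in the group of 22 fits the stated 93%.

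**Step 1: reproduce the stated power.** The unequal-variance SE is √(30²/n₁ + 15²/n₂).

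- Cohort 1: √(56.25 + 1.5625) = 7.60, Satterthwaite df 15.8.
- Cohort 2: √(40.91 + 4.33) = 6.73, df 25.6.

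| Test, difference 24 | Cohort 1 (stated 86%) | Cohort 2 (stated 93%) |
|---|---|---|
| Welch, two-sided | 84.1% | 92.9% |
| Welch, one-sided | 91.5% | 96.6% |
| Student, two-sided, data with SDs 30/15 | 97.7% | 97.7% |

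Two-sided Welch is the only row near both stated figures. With 17 against 143 in cohort 1 it gives 86.5%.

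**Step 2: the standard error that Student's test uses.** Pooled SE = √{[(n₁−1)·900 + (n₂−1)·225]/(n₁+n₂−2)} × √(1/n₁ + 1/n₂).

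- Cohort 1: √[(15·900 + 143·225)/158] × √(1/16 + 1/144) = 17.00 × 0.2635 = 4.48. True SE / pooled SE = 7.60/4.48 = 1.697.
- Cohort 2: √[(21·900 + 51·225)/72] × √(1/22 + 1/52) = 20.54 × 0.2543 = 5.22. Ratio 6.73/5.22 = 1.288.

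**Step 3: rejection rate with equal means.** Large-sample approximation, with Φ the standard normal distribution function:

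- Two-sided, 2Φ(−1.96/ratio): 24.8% and 12.8%.
- One-sided, Φ(−1.645/ratio): 16.6% and 10.1%.

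Numerical integration over the two sample variances, with normal data and Student's test at nominal 5%, gives:

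| True SDs (event / non-event) | Two-sided, cohort 1 / 2 | One-sided, cohort 1 / 2 |
|---|---|---|
| 30 / 15 | 24.7% / 12.8% | 16.6% / 10.1% |
| 22.5 / 15 | 15.4% / 9.4% | 11.6% / 8.0% |
| 18.75 / 15 | 10.1% / 7.3% | not computed |
| equal | 5.0% / 5.0% | 5.0% / 5.0% |
| 15 / 30 | 0.1% / 1.3% | 0.3% / 1.8% |

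The one-sided entries in the last two rows come from simulation. A simulation of 1,000,000 trials per case gave 24.6% and 12.8% two-sided at 30/15, and 16.6% and 10.1% one-sided. Welch's test stayed between 5.0% and 5.1% throughout. The rates depend only on the SD ratio and the group sizes: SDs of 20/10 give the same result, so the common 50% inflation is irrelevant here.

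**Step 4: intervals.** A Student 95% interval covers the true difference 100 − 24.7 = 75.3% of the time in cohort 1 and 100 − 12.8 = 87.2% in cohort 2, whatever that difference is. Half-widths at the planning SDs, Student against Welch, are 8.8 against 16.1 (cohort 1) and 10.4 against 13.8 (cohort 2).

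**Step 5: the synopsis test.** The t-test of a Pearson correlation between a continuous variable and a binary one is algebraically Student's pooled t-test, so the same rates apply.

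**The case against.** The strongest objection is about the null. The SDs of 30 and 15 are given together with a 24-unit difference, so they describe the alternative. If perfusion is unrelated to SSI, both groups share one distribution, the SDs are equal and Student's test holds 5%. That is true and limits the finding. But the stated nulls concern the level of I_max-post, and equal means with unequal spread is compatible with them. The loss of interval coverage needs no null at all: it applies equally at the planned 24-unit difference.

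Second, authors often write Student's t-test for any two-sample t-test, and the power figures suggest that unequal variances were allowed for. That may be so, but an analyst following section 7.2 would run the pooled test, and the Pearson test in the synopsis is the pooled test on any reading. In cohort 1 alone, a pooled test with a common SD of 30 gives 85.5%, closer to 86% than Welch. It gives 87.4% in cohort 2 against 93%, so Welch remains the better joint fit.

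Third, half of the two-sided rejections point away from the hypothesis. Counting only those in the hypothesised direction, the rates are 12.4% and 6.4% against a nominal 2.5%. That is still about 5 and 2.6 times too many.

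Fourth, the SDs are porcine values for I_max, while the t-test is applied to whichever variable has the highest AUC. If another variable is chosen, the documents give no SD ratio for it. This stands as a condition on the size.

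Fifth, Welch holds 5% for normal data only. Assuming gamma or lognormal intensities with means of 40 to 80 a.u. (not in the documents) and SDs 30/15, Welch rejects about 6% to 9% two-sided in cohort 1. Student's test rejects about 24% to 25% in the same cases. With equal SDs and skewed data, Student's test is the closer of the two to 5%.

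**Conclusion.** The concern holds. Under section 7.1's own SDs and group sizes, with normal data and the name read as the pooled test, Student's t-test does not hold the stated 5%. With equal means it rejects about 25% and 13% of the time two-sided, or 17% and 10% one-sided, in cohorts 1 and 2. The named test also does not match the calculation behind the stated power.

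The size rests on the 2:1 SD ratio with the larger SD in the smaller group. A ratio of only 1.25 still doubles the cohort 1 rate to about 10%. Equal SDs remove the excess, and the reverse order makes the test conservative. This is a Phase I pilot that does not alter care, but it tests stated primary hypotheses at 5%, so the wording should be corrected before analysis.

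**What to change.** - In section 7.2 and Tables 7.1 and 7.2, name Welch's unequal-variance t-test, with Welch confidence intervals for the mean difference.
- State the sidedness once. Two-sided agrees with the synopsis and with the power figures.
- Do not use the synopsis t-test of the Pearson correlation for inference.
- Restate cohort 1 power as about 84% for 16 against 144. Cohort 2 stays at 93%.

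The cost is wording: no extra patients or data, and about 2 points off the stated cohort 1 power. If the human SDs turn out equal and the data are near normal, Welch still holds 5%.

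This corrects the unadjusted comparison of means only. It does not address selecting the variable by highest AUC before testing, or the logistic Wald test. In a univariable logistic model under the same inputs, simulation gave about 23% and 11% two-sided; the plan's multiple model was not evaluated.
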